6.2 Everolimus Dose Modifications Due to Non-Hematologic Toxicity

Dose reductions and management of non-hematologic toxicities related to everolimus are defined in Table 3 and Table 4.

CONFIDENTIAL

STUDY DRUG(S): EVEROLIMUS
FINAL PROTOCOL DATE: 19 JUNE 2014

SCRI INNOVATIONS STUDY NUMBER: BRE 212
VERSION 1.0

Table 3 Everolimus Dose Modifications and Management of Hepatic Toxicity

Toxicity	Actions
AST or ALT elevation Grade 3 (> 5.0 - 20.0 ULN)*	Interrupt everolimus administration until resolution to \leq Grade 1 (or \leq Grade 2, if baseline values were within the range of Grade 2). If resolution occurs \leq 7 days, reintroduce everolimus at the dose level prior to interruption. If resolution occurs > 7 days, or if event recurs within 28 days, hold everolimus until recovery to \leq Grade 1 or baseline value and reintroduce everolimus at one dose level lower, if available.
AST or ALT elevation Grade 4 (> 20 x ULN)*	Interrupt everolimus administration until resolution to \leq Grade 1 (or \leq Grade 2, if baseline values were within the range of Grade 2). If resolution occurs \leq 7 days, reintroduce everolimus at one dose level lower. If resolution occurs > 7 days, discontinue everolimus.
Recurrence of Grade 4 after dose reduction or toxicity requiring Everolimus interruption for > 28 days	Discontinue everolimus.
Grade 3 or 4 clinical liver failure (asterixis or encephalopathy/coma)	Discontinue everolimus.

* Should HCV flare be confirmed, the guidelines for flare must take precedence (See Section 6.2.10).

CONFIDENTIAL

STUDY DRUG(S): EVEROLIMUS
FINAL PROTOCOL DATE: 19 JUNE 2014

SCRI INNOVATIONS STUDY NUMBER: BRE 212
VERSION 1.0

Table 4 Everolimus Dose Modifications and Management of Non-Hematologic Toxicity

Toxicity	Actions
Intolerable Grade 2 mucositis, or Grade 3 AE (except pneumonitis [see Table 5] and except hyperglycemia or hypercholesterolemia [See Section 6.2.5])	Interrupt everolimus administration until resolution to \leq Grade 1 or baseline value. If resolution occurs within \leq 7 days, reintroduce everolimus at the dose level prior to interruption. If resolution occurs $>$ 7 days, or if event recurs within 28 days, hold everolimus until recovery to \leq Grade 1 or baseline value and reintroduce everolimus at one dose level lower, if available. Patients will be withdrawn from the study if they fail to recover to \leq Grade 1 or baseline value within 28 days.
Recurrence of Grade 2 mucositis or Grade 3 AE after dose reduction	Reduce dose to the next lower dose level, if available. The lowest possible dose level of everolimus is 5 mg every other day (2.5 mg daily). Below this level, everolimus must be discontinued. If toxicity recurs at Grade 3, consider discontinuation.
Grade 4 AE	Hold everolimus until recovery to \leq Grade 1 or baseline value. Reintroduce everolimus at one dose level lower, if available.
Grade 4 AE recurrence after dose reduction	Discontinue everolimus.
Any non-hematologic toxicity requiring interruption for $>$28 days.	Discontinue everolimus.

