6.1 Dose Modifications Due to Hematologic Toxicity

Dose modifications on Day 1 of each cycle will be based on blood counts determined on the day of scheduled treatment. Nadir blood counts will not be used to determine dose modifications. Treatment on Day 1 of any cycle will proceed if blood counts demonstrate ANC $\geq 1.5 \times 10^9/L$ and platelets $\geq 100 \times 10^9/L$ (See Table 2).

CONFIDENTIAL

STUDY DRUG(S): EVEROLIMUS
FINAL PROTOCOL DATE: 19 JUNE 2014

SCRI INNOVATIONS STUDY NUMBER: BRE 212
VERSION 1.0

Table 2 Everolimus Dose Modifications Due to Hematologic Toxicities

Toxicity	Actions
Grade 3 thrombocytopenia (platelets <50, $\geq 25 \times 10^9/L$)	Interrupt everolimus until resolution to \leq Grade 1. If AE resolution occurs \leq 7 days, reintroduce everolimus at the dose level prior to interruption. If AE resolution occurs $>$ 7 days, or event recurs within 28 days, reintroduce everolimus at one dose level lower, if available.
Grade 4 thrombocytopenia (platelets < $25 \times 10^9/L$)	Interrupt everolimus until recovery to \leq Grade 1. Then reintroduce everolimus at one dose level lower, if available.
Grade 3 Neutropenia (neutrophils $<1, \geq 0.5 \times 10^9/L$) or Grade 3 anemia (Hgb <8.0-6.5g/dL; <4.9-4.0 mmol/L; <80-65 g/L; transfusion indicated.)	Interrupt everolimus until resolution to \leq Grade 1 or baseline value. If AE resolution occurs \leq 7 days, reintroduce everolimus at the same dose level. If AE resolution occurs $>$ 7 days, or event occurs within 28 days, reintroduce everolimus at one dose level lower, if available.
Grade 4 Neutropenia (neutrophils $<0.5 \times 10^9/L$) or Grade 4 anemia (Life-threatening consequences; urgent intervention indicated.)	Interrupt everolimus until recovery to \leq Grade 1 or baseline value. Reintroduce everolimus at one dose level lower, if available.*
Febrile Neutropenia	Interrupt everolimus until resolution to \leq Grade 1 (or baseline value) and no fever. Reintroduce everolimus at one dose level lower, if available.*
Grade 3 AE recurrence after dose reduction	Interrupt everolimus until resolution to \leq Grade 1. Reduce dose to the next lower dose level, if available. The lowest possible dose level of everolimus is 5 mg every other day (2.5 mg daily). Below this level, everolimus must be discontinued.

*Grade 4 AE recurrence (including febrile neutropenia) after dose reduction, discontinue everolimus.

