*Any hematologic toxicity requiring everolimus interruption for $>$ 28 days, discontinue everolimus.

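### Table 3 gives two recovery thresholds for the same Grade 3 AST/ALT hold, which disagree for patients with liver metastases and Grade 2 baseline enzymes; Table 2 has a narrower mismatch for recurrent anemia

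*Protocol*

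**What the plan says.** **Table 3 (Protocol Section 6.2), row "AST or ALT elevation Grade 3 (> 5.0 - 20.0 ULN".** The cell has two recovery conditions.

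- First sentence: interrupt until the value is Grade 1 or better, or at most "Grade 2, if baseline values were within the range of Grade 2". If that takes 7 days or less, the previous dose is resumed.
- Last sentence: if resolution takes longer than 7 days, or the event returns within 28 days, hold until at most "Grade 1 or baseline value and reintroduce everolimus at one dose level lower, if available".

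A later row, "Recurrence of Grade 4 after dose reduction or toxicity requiring Everolimus interruption for > 28 days", leads to stopping everolimus. The Grade 4 AST/ALT row has a single recovery threshold.

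**Table 2 (Protocol Section 6.1).** The Grade 3 neutropenia/anemia row accepts recovery to at most "Grade 1 or baseline value. If AE resolution occurs", and the same row also covers a further event: "event occurs within 28 days, reintroduce everolimus at one dose level lower, if available". The Grade 4 neutropenia/anemia and febrile neutropenia rows also accept baseline. The row for Grade 3 recurrence following a dose reduction requires at most "Grade 1. Reduce dose to the next lower dose level, if available", with no mention of baseline. A footnote, "Any hematologic toxicity requiring everolimus interruption for" more than 28 days, stops everolimus.

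**Eligibility (Section 3.1).** Criterion 9 admits AST/ALT up to 2.5 x ULN, or up to 5 x ULN with liver metastases. Criterion 8 admits hemoglobin above 9 g/dL.

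**The concern.** A recovery rule should give one answer for one laboratory value. In the Table 3 row, a patient can count as resolved under the first sentence and as not yet recovered under the last, on the same day and with the same result. One investigator may restart everolimus. Another may keep holding, and if the value does not move, the 28-day rule then removes the drug. With about nine sites (Section 5), uneven application is plausible.

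The first thing at stake is consistent patient management. The second is the tolerability result: safety and tolerability is a secondary endpoint (Section 2.4), and the SAP's adverse event overview (Table 10) counts events leading to discontinuation, interruption and dose reduction. Those counts would partly reflect which sentence a site followed.

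**Working it through.** The plan states no figure on this point. The check is to write each recovery condition as a logical test and list the values on which the tests disagree.

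**Table 3, Grade 3 AST/ALT.** Let v be the current value, b the baseline and c the upper limit of Grade 1, all in multiples of ULN.

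- Grade 3 is printed as starting above 5.0, so Grade 2 ends at 5.0.
- The documents do not print c. I assume 2.5 to 3.0.
- First sentence is met if v ≤ c, or if c < b ≤ 5.0 and v ≤ 5.0.
- Last sentence is met if v ≤ c, or if v ≤ b (reading baseline value as a number).
- They disagree exactly when c < b < v ≤ 5.0.

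Results, the same for c = 2.5 and c = 3.0:

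| Baseline (x ULN) | Values meeting the first sentence and failing the last |
|---|---|
| 2.0 or 2.5 | none |
| 3.1 | above 3.1, up to 5.0 |
| 3.5 | above 3.5, up to 5.0 |
| 4.0 | above 4.0, up to 5.0 |
| 4.5 | above 4.5, up to 5.0 |
| 5.0 | none |

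All patients without liver metastases enter at 2.5 or below, so none of them is affected.

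Worked example: a patient has baseline 3.5, rises to 6 (Grade 3), then sits at 4.5 from day 10.

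- First sentence: 4.5 ≤ 5.0 and baseline was Grade 2, so the event resolved on day 10.
- Day 10 is later than day 7, so the last sentence applies. It requires v ≤ 3.5, and 4.5 fails.
- If 4.5 persists beyond 28 days of interruption, the 28-day row discontinues everolimus.

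Had the value reached 4.5 by day 7, the first sentence and the 7-day branch would agree on restart. The clash is confined to later resolution, or to recurrence within 28 days.

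**Table 2, anemia.** Let h be current hemoglobin, b baseline and f the Grade 1 floor, in g/dL.

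- Grade 3 row is met if h ≥ f or h ≥ b.
- Recurrence row is met if h ≥ f.
- They disagree when b ≤ h < f, which needs b < f.

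The documents do not print f, so I take 9.0 to 10.0. For a baseline of 9.1:

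- f = 10.0: they disagree from 9.1 to just under 10.0.
- f = 9.5: they disagree from 9.1 to just under 9.5.
- f = 9.0: no disagreement.

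A baseline at or above the floor gives no disagreement at any setting. Both rows describe the same event only when Grade 3 anemia returns within 28 days and after a dose reduction.

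**Scale.** Protocol Section 1.2 reports 6% Grade 3 or 4 anemia with the combination in the cited Phase III trial: 46 x 0.06 = 2.8 patients before any narrowing. Only those with a baseline below the floor, a prior reduction, a prompt recurrence and a value remaining between baseline and floor for more than 28 days would be exposed. No AST/ALT rate is given, so the liver side cannot be sized. One patient is 1/46 = 2.2 percentage points of a discontinuation rate; this is a unit of scale and not an effect estimate.

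**The case against.** **Baseline value may mean baseline grade.** On that reading, the two Table 3 conditions agree and nothing needs fixing. The reading is possible but strained. Where the row means grade, it says so. Table 7 uses a baseline HBV-DNA value as a number. SAP Section 3 defines baseline as the last value before treatment, although that definition serves the analysis and not dosing. The corresponding row of Table 4 has the same structure and uses one threshold in both places, which suggests a drafting mismatch in Table 3.

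**The branches are sequential, and a stricter test for slow recovery may be intended.** This has some force: an investigator could let the last sentence govern after day 7. But the row does not say so, and the first sentence has by then already ended the interruption.

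**The Table 2 rows cover different situations.** This largely stands. A recurrence row can deliberately be stricter, and the same table stops everolimus when a Grade 4 event recurs. What remains is the narrow overlap, plus the oddity that a first Grade 4 anemia may restart at baseline while a recurrent Grade 3 may not.

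**A patient enrolled at 9.5 g/dL is not locked out.** A reader might infer that such a patient can never satisfy the recurrence row and must stop. The documents do not support this: Section 5.4 permits transfusion, and the Grade 1 floor is itself an assumption.

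**Conclusion.** The Table 3 contradiction holds, in a limited form. It concerns the Grade 3 AST/ALT row only, in patients with liver metastases whose baseline is Grade 2 and below 5.0 x ULN, when resolution takes more than 7 days or the event returns within 28 days. It assumes that baseline value is read as a number and that Grade 1 ends somewhere from 2.5 to 3.0 x ULN. The consequence ranges from restart to discontinuation of everolimus; under Section 6, anti-estrogen therapy may continue. The Table 2 difference is secondary and may be intended.

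Few patients are affected, and the number cannot be computed from the documents. Three broader inferences are not supported:

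- That every patient with raised liver enzymes is exposed. Those without liver metastases are not.
- That the resulting stops would be mistaken or avoidable. This presumes the more permissive threshold is right, which the documents do not establish.
- That the primary result is distorted. The SAP's PFS table does censor at treatment discontinuation for an adverse event, so an effect is conceivable. But the documents do not say whether stopping everolimus alone counts as treatment discontinuation, and no size can be derived.

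**What to change.** - Reconcile the first and last sentences of the Table 3 Grade 3 AST/ALT row so that one recovery definition applies throughout, and state whether baseline means the number or the grade.
- Reconcile the Table 2 row on Grade 3 recurrence after a dose reduction with the Grade 3 anemia row, or confirm that the difference is intended and say which row governs where they overlap.

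Which threshold applies is the sponsor's clinical decision. The cost is wording in two table rows, with no change to sample size or analysis.

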3.3 Discontinuation from Study Treatment

Patients will be discontinued from study treatment for any of the following reasons:

- Disease progression.
- Irreversible or intolerable toxicity or abnormal laboratory values.
- Patient requests to withdraw from the study and discontinue treatment.
- Inability of the patient to comply with study requirements.
- Conditions requiring therapeutic intervention not permitted by the protocol.
- Intercurrent illness (this will be at the investigator's discretion).
- Non-compliance or lost to follow-up.

After discontinuation from protocol treatment, patients must be followed for AEs for 30 calendar days after their last dose of study drug. All new AEs occurring during this period must be reported and followed until resolution, unless, in the opinion of the investigator, these values are not likely to improve because of the underlying disease. In this case, the investigator must record his or her reasoning for this decision in the patients' medical records and as a comment on the electronic Case Report Form (eCRF).

All patients who have Grade 3 or 4 laboratory abnormalities (Common Terminology Criteria for Adverse Events [CTCAE] v4.0 (<http://evs.nci.nih.gov/ftp1/CTCAE/CTCAE>) at the time of discontinuation must be followed until the laboratory values have returned to Grade 1 or 2, unless it is, in the opinion of the investigator, not likely that these values are to improve. In this case, the investigator must record his or her reasoning for making this decision in the patients' medical records and as a comment on the CRF.

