6. DOSE MODIFICATIONS

All toxicities will be graded utilizing the NCI CTCAE v 4.0 (<http://evs.nci.nih.gov/ftp1/CTCAE/CTCAE>). If toxicity occurs, the toxicity will be graded, and appropriate supportive care treatment will be administered to decrease the signs and symptoms thereof. Dose adjustments will be based on the organ system exhibiting the greatest degree of toxicity.

Adverse events most frequently observed with everolimus are rash, stomatitis/oral mucositis, non-infectious pneumonitis, fatigue, headache, anorexia, nausea, vomiting, diarrhea, and infections. Overall, the most frequently observed laboratory abnormalities include neutropenia, thrombocytopenia, hyperglycemia, hypercholesterolemia, and/or hypertriglyceridemia. The majority of these AEs have been of mild to moderate severity (NCI CTCAE Grade 1-2).

The dose level reductions for everolimus to be used in this study are shown in Table 1.

If everolimus is interrupted for any reason, and the patient has no toxicity related to anti-estrogen therapy, the patient should continue anti-estrogen therapy per schedule. If the patient discontinues everolimus for any reason, they should continue to receive anti-estrogen therapy if patient is deriving clinical benefit from the therapy.

Table 1 Everolimus Dose Level for Toxicity

Dose Level	Everolimus
Starting Dose	10 mg daily
Dose Level -1	5 mg daily
Dose Level -2	5 mg every other day

No more than 2 dose reductions for everolimus are permitted. Patients who need an additional dose reduction will be required to discontinue everolimus.

Table 2 lists the dosing guidelines for everolimus-related hematologic toxicities, Table 3 and Table 4 list the dosing guidelines for everolimus-related non-hematologic toxicities.

CONFIDENTIAL

STUDY DRUG(S): EVEROLIMUS
FINAL PROTOCOL DATE: 19 JUNE 2014

SCRI INNOVATIONS STUDY NUMBER: BRE 212
VERSION 1.0

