Grade 3 (Symptomatic, Interfering with Activities of Daily Living. O ₂ indicated)	CT scan with lung windows and pulmonary function testing including: spirometry, DLCO, and room air O ₂ saturation at rest. Consider a bronchoscopy with biopsy and/or BAL. Monitor at each visit until return to ≤ Grade 1. Return to initial monitoring frequency if no recurrence.	Consider corticosteroids if infective origin is ruled out. Taper as medically indicated.	Rule out infection and interrupt everolimus until symptoms improve to ≤ Grade 1. Consider reintroducing everolimus at one dose level lower. Discontinue everolimus if failure to recover within ≤ 28 days. If toxicity recurs at Grade 3, consider discontinuation.
Grade 4 (Life-threatening, ventilatory support indicated)	CT scan with lung windows and required pulmonary function testing, if possible, including: spirometry, DLCO, and room air O ₂ saturation at rest. Bronchoscopy with biopsy and/or BAL is recommended if possible. Monitor at each visit until return to ≤ Grade 1. Return to initial monitoring frequency if no recurrence.	Consider corticosteroids if infective origin is ruled out. Taper as medically indicated.	Rule out infection and discontinue everolimus.

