7.4 Response Assessment Every 2 Cycles

Patients will be reevaluated for response to treatment after every 2 cycles of treatment, prior to the start of odd-numbered cycles. The following assessments will be performed:

- CT scans of chest
- CT of abdomen and pelvis
- Bone scan (if abnormal at baseline)

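### The SAP's PFS censoring row for stopping treatment makes no exception for progression or death seen later; a lesser wording conflict in Protocol Table 4 should be cleared with it

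*Protocol*

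**What the plan says.** **PFS in the SAP.** The PFS definition is the same in Protocol 10.4.2 and SAP 1.2. Progression or death on study is an event. Three groups are censored: patients alive and progression-free, patients who start non-protocol therapy before an event, and patients with no post-baseline tumor assessment. The table in SAP Section 4 turns this into situations. Its last row adds one that the definition lacks: a patient who stops treatment for an adverse event or other non-event reason is censored at the last evaluable tumor assessment. The row carries no condition, and the table gives no order of precedence. The row just above it already censors, on the same date, patients with neither progression nor death.

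**Non-recovery at 28 days in the protocol.** Table 4, row 1, covers intolerable Grade 2 mucositis and most Grade 3 adverse events. It ends: "Patients will be withdrawn from the study if they fail to recover to" Grade 1 or baseline within 28 days. The last row of the same table reads "Any non-hematologic toxicity requiring interruption for" more than 28 days, and its action is to discontinue everolimus. Section 6 adds: "If the patient discontinues everolimus for any reason, they should continue to receive anti-estrogen therapy if patient is deriving clinical benefit from the therapy".

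**The concern.** PFS is the primary endpoint. Protocol 7.6.1 follows patients who stop before progression every 3 months until progression or 3 years, and SAP Section 4 lists that follow-up among its efficacy timepoints. Applied as written, the last SAP row would set aside the progressions and deaths that this follow-up exists to collect. Two programmers could code the same patient differently, and nothing in the SAP says which is right. In an open-label, single-arm trial that choice should be settled before the data are analyzed.

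The Table 4 conflict touches the same endpoint less directly. Under the last row, a patient who is benefiting stays on anti-estrogen therapy and is scanned on the treatment schedule ("Patients will be reevaluated for response to treatment after every 2 cycles of treatment, prior to the start of odd-numbered cycles", that is, every 8 weeks). A site that follows row 1 may stop both drugs and move the patient to 3-monthly assessments.

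**Working it through.** **1. Does the SAP row overlap with an event row?** Take a patient who stops both drugs for toxicity, starts no other therapy, and is found to have progressed at a later follow-up visit.

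- Definition (Protocol 10.4.2, SAP 1.2): event on the date of progression.
- Progression row without subsequent therapy (SAP Section 4): event.
- Last row: censored at the last evaluable assessment. It does not say whether that means the last one before stopping.

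A patient who dies on study without progression or new therapy meets the same conflict with the death row. For a patient with no later event, the last row repeats the row above it. It therefore changes a result only when it censors an observed event.

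**2. The plan's own figure.** Protocol 10.2 gives N = 42 for a median of 2.8 versus 5 months, one-sided 5% alpha and 80% power. With exponential survival, S(2.8) = 0.5^(2.8/5) = 0.678. Then n = (1.645 + 0.842)² × 0.678 × 0.322 / (0.678 − 0.5)² = 42.4 before rounding of the inputs, and power at 42 is 79.6%. The figure reproduces and is not in dispute.

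**3. Size of the bias under the literal reading.** Neither document gives a discontinuation rate or the risk after stopping, so both are assumed: a share p of 5–20% is censored before progression, and the later hazard is HR = 0.7 to 2 times that of the rest.

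- Reported median 5.0 months, so λ = ln 2 / 5 = 0.1386 per month.
- Constant stopping hazard g = pλ/(1 − p), so that a share p stops before progression.
- True survival S(t) = exp(−(λ+g)t) + ∫₀ᵗ g·exp(−(λ+g)u)·exp(−HR·λ(t−u)) du; solve S(t) = 0.5.
- Example, p = 20% and HR = 2: g = 0.0347. At t = 4.70 the first term is 0.443 and the integral 0.057, which sum to 0.500.

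As a check on timing, let a share p of those still at risk all stop at the 8-week scan (1.84 months).

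| Stopping pattern | p | HR 0.7 | HR 1 | HR 1.5 | HR 2 |
|---|---|---|---|---|---|
| Constant | 5% | 5.03 | 5.00 | 4.96 | 4.93 |
| Constant | 10% | 5.06 | 5.00 | 4.92 | 4.86 |
| Constant | 20% | 5.14 | 5.00 | 4.83 | 4.70 |
| All at 8 weeks | 10% | 5.10 | 5.00 | 4.86 | 4.76 |
| All at 8 weeks | 20% | 5.21 | 5.00 | 4.73 | 4.54 |

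Entries are true medians in months when 5.0 is reported. Reported minus true runs from −0.21 to +0.46. For comparison, 200,000 simulated samples of 42 uncensored exponential times with median 5 give a 95% range of 3.16–7.48 months for the sample median.

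**4. Loss of information.** A separate simulation used n = 42, a true median of 5, and 10%, 20% or 30% assigned to stop at 1–4 months if still progression-free, censored back to the previous 8-week scan (1,500 runs each). Mean events fell from 42 to about 39, 36 and 33. With the later hazard unchanged, power was 72%, 69% and 60%, against 73–76% when later events were counted. Back-dating to the previous scan has a small effect of its own, which the formula in step 3 leaves out: at 30% and an unchanged hazard, the typical median read 4.64 rather than 4.80.

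**5. The 28-day rules in the protocol, side by side.**

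- Table 4, row 1: withdrawn from the study.
- Table 4, last row: discontinue everolimus.
- Table 2 footnote, "Any hematologic toxicity requiring everolimus interruption for" more than 28 days: discontinue everolimus.
- Table 3, "Recurrence of Grade 4 after dose reduction or toxicity requiring Everolimus interruption for" more than 28 days: discontinue everolimus.
- Table 5, Grades 2 and 3: "Discontinue everolimus if failure to recover within" 28 days.
- Table 7, hepatitis B reactivation not resolved by 28 days: discontinue everolimus.

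Row 1 is the only one that goes beyond everolimus, and a patient with Grade 3 fatigue unresolved at day 29 fits both it and the last row.

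**The case against.** On the SAP row, the strongest reply is that its label points to patients without an event, and that the definition, stated in both documents, settles any doubt. A redundant row proves little in a checklist: the OS table also lists two situations with the same outcome. That is a fair account of what was probably intended. But the label qualifies the reason for stopping, not what happens later. Other rows spell out their conditions on prior progression and subsequent therapy; this one has none. The drafting fault stands whatever the intent.

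A reader might also infer that the row flatters everolimus. The documents do not support that. The direction depends on the hazard after stopping, which they do not give.

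On Table 4, a reader might infer that row 1 ends follow-up and loses progression and survival data. The documents point the other way. Section 3.3 ("Patients will be discontinued from study treatment for any of the following reasons") treats intolerable toxicity as a reason to leave treatment. Section 7.6.1 follows patients who stop before progression. Appendix D footnote k speaks of leaving the study but times the visit from the end of treatment, and footnote m follows survival whatever the reason for stopping. This part of the objection stands. Only anti-estrogen continuation and the scan interval remain open.

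The Grade 3 or 4 rates quoted in Protocol 1.2 cannot anchor the size. They combine two grades that Table 4 handles separately, include stomatitis (which has its own rules in 6.2.6), and say nothing about non-recovery. The arithmetic above sizes the SAP row only.

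**Conclusion.** The SAP row is wrong as written: taken literally, it censors observed events that the stated PFS definition counts. Under the assumed 5–20% censoring and hazard ratio of 0.7–2, a reported 5.0-month median stands for a true median of about 4.5–5.2 months. The direction is unknown, the formula gives no bias at a ratio of 1, and the shift is small against sampling error. The extreme of +0.46 months needs 20% of those at risk to stop at one scan and then progress at twice the rate.

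The Table 4 wording is a real but secondary conflict, limited to whether anti-estrogen therapy and 8-week scans continue. Its effect on PFS has not been sized. Severity for both: minor.

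**What to change.** **SAP Section 4, PFS table.** Delete the last row, or limit it to patients who stop for an adverse event or other non-event reason and have no later progression or death before subsequent therapy, censored at the last evaluable tumor assessment. State that progression or death observed after stopping and before subsequent therapy is an event on its date. This costs one row; the follow-up data are already scheduled, and sample size and alpha do not change.

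**Protocol Table 4, row 1.** Replace the last sentence with: Discontinue everolimus if not recovered to Grade 1 or baseline within 28 days; continue anti-estrogen therapy with scans every 2 cycles if benefiting (Section 6), otherwise follow per Section 7.6.1; survival follow-up per Appendix D footnote m. Footnote m is the right reference because Section 7.6.2 begins only after documented progression. Section 14.1 requires sponsor, supporting-company, investigator and IRB review of an amendment, so this can go in with the next one. No visits or scans are added.

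### Table 4's recurrence row lowers the everolimus dose without stating an interruption, while Table 4's first row and Section 6.2.6 require one for events that also match, and no precedence is given.

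*Protocol*

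**What the plan says.** Four places in protocol Section 6 bear on this.

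- **Table 4, recurrence row.** The trigger is "Recurrence of Grade 2 mucositis or Grade 3 AE after dose reduction". The action is "Reduce dose to the next lower dose level, if available", with everolimus stopped if no lower level remains. The row ends: "If toxicity recurs at Grade 3, consider discontinuation". It mentions no interruption and no recovery level.
- **Table 4, first row.** It covers intolerable Grade 2 mucositis and Grade 3 events, apart from listed exceptions, and is not confined to first occurrences. The instruction is "Interrupt everolimus administration until resolution to \leq Grade 1 or baseline value". The previous dose resumes if the event resolves within 7 days. If resolution is slower, "or if event recurs within 28 days, hold everolimus until recovery to" the same threshold, and everolimus then restarts one level lower.
- **Section 6.2.6.** Its stomatitis table has everolimus interrupted when Grade 2 stomatitis recurs, until it improves to Grade 1 or below, and then restarted at a lower dose.
- **Table 2, row for Grade 3 recurrence after a reduction.** It writes both steps: "Interrupt everolimus until resolution to \leq Grade 1. Reduce dose to the next lower dose level, if available". Section 6 confines Table 2 to hematologic toxicity.

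Neither Section 6 nor Section 6.2 says which Table 4 row takes priority when two match, or how Table 4 ranks against Section 6.2.6.

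**The concern.** A Grade 3 event that returns after a dose reduction meets both Table 4 triggers: it is a Grade 3 event, and it is a recurrence after a reduction. A site that follows the recurrence row as written lowers the dose and finds no instruction to hold. A site that follows the first row holds, and may then return to the same dose. Recurrent Grade 2 mucositis raises the same question between the recurrence row and Section 6.2.6.

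The patients concerned have already needed one reduction, so this is first a safety matter. It also touches the secondary objective of safety and tolerability. SAP Table 5 counts dose reductions and interruptions, and SAP Table 10 counts adverse events leading to discontinuation, interruption or reduction. With about 9 sites and no data monitoring committee, different readings could persist unnoticed and those counts would mix them.

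**Working it through.** The plan gives no figure to reproduce, so the main check sets the passages side by side. A short sizing follows.

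**Step 1: which events are in scope.** Events with their own rules are left out: pneumonitis (Table 5), hyperglycemia and hypercholesterolemia (excepted in Table 4's first row), AST/ALT elevation (Table 3), hepatitis B reactivation (Table 7) and hepatitis C flare (Table 8). What remains includes Grade 3 fatigue, dyspnea and renal events (the last sent to Table 4 by Section 6.2.5), and recurrent Grade 2 mucositis, where Section 6.2.6 also applies.

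**Step 2: follow one patient through each passage.** Suppose the dose has already been reduced once, from 10 mg daily to 5 mg daily (Table 1), and the toxicity returns.

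| Event after the reduction | Table 4, first row | Table 4, recurrence row | Section 6.2.6 |
|---|---|---|---|
| Grade 3, recurs within 28 days | Hold to Grade 1 or baseline, then 5 mg every other day | 5 mg every other day; no hold stated | Not applicable |
| Grade 3, recurs after 28 days, resolves in more than 7 days | Hold, then 5 mg every other day | 5 mg every other day; no hold stated | Not applicable |
| Grade 3, recurs after 28 days, resolves within 7 days | Hold, then 5 mg daily again | 5 mg every other day; no hold stated | Not applicable |
| Grade 2 mucositis or stomatitis recurs | Hold, if judged intolerable; restart dose as for Grade 3 above | 5 mg every other day; no hold stated | Interrupt to Grade 1 or below, then a lower dose |

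In the first two lines the rows agree on the restart dose and differ only in whether a hold is written. In the third they differ on both. In the fourth, the recurrence row and Section 6.2.6 agree on a lower dose and differ on the interruption.

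The third line has a further consequence at the lowest level, 5 mg every other day. There the first row returns the patient to that dose, while the recurrence row has no lower level left and leads to discontinuation.

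**Step 3: the closing sentence.** A Grade 3 recurrence is one of the row's own triggers, so the sentence could mean that event or a later one after the further step-down. It could also separate Grade 3 from Grade 2 mucositis. The row does not say.

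**Step 4: a link to the 28-day rule.** Table 4's last row stops everolimus when a non-hematologic toxicity requires interruption for more than 28 days. If the recurrence row calls for no interruption, it is unclear whether that limit applies.

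**Step 5: size, for illustration.** Inputs: 46 patients (Section 5). Grade 3 or 4 rates in the everolimus arm of the randomized phase III trial with exemestane (Section 1.2): dyspnea 4%, fatigue 4%. Stomatitis (8%) is left out because Section 6.2.6 gives it its own instructions.

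- First events, assuming no overlap: 46 × (0.04 + 0.04) = 46 × 0.08 = 3.7, about 4 patients.
- Recurrence share: 20% to 50%, an assumption, since the documents give none.
- Recurrences: 3.7 × 0.20 = 0.7 and 3.7 × 0.50 = 1.8, about 1 to 2 patients.
- One patient in a descriptive rate: 1/46 = 2.2 percentage points.

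This is not a bound. It covers only two of the commonest events and no Grade 2 mucositis, which would raise it. It includes Grade 4 events, which have separate rows, and first events that did not lead to a reduction, which would lower it.

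**The case against.** The strongest reply is that silence is not contradiction. A recurrent Grade 3 event is still a Grade 3 event, so the first row's hold can carry over and the recurrence row can simply fix the restart level. Nothing in the recurrence row forbids a hold. That is a coherent reading, and it rules out a stronger inference: that the protocol orders dosing through active Grade 3 toxicity. It does not. The reply still falls short, because no sentence joins the rows. It also does not settle the restart dose when a late recurrence resolves quickly.

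A reader might also infer three competing instructions by counting Table 2. Table 2 applies only to hematologic toxicity, so it is a wording comparison: it shows that a parallel row writes the hold out, and nothing more.

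Nor is the closing sentence necessarily circular. Table 5 uses the same wording for pneumonitis after re-introduction at a lower level, which supports reading it as a later recurrence. The word consider also allows investigators to differ legitimately. What stands is only that the intended recurrence is not identified.

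Finally, the affected SAP tables are descriptive and no test depends on them. That is correct and limits the weight of the point.

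**Conclusion.** The point holds as an internal inconsistency, with moderate confidence. For the same recurrent event, the recurrence row as written gives a different action from Table 4's first row, and for Grade 2 mucositis a different one from Section 6.2.6. The protocol states no order of precedence. The conflict is confined to events that meet more than one trigger and have no separate rule of their own.

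The likely number is small, about 1 to 2 of 46 patients on the assumptions shown. What is affected is the handling of those patients and the descriptive counts in SAP Tables 5 and 10. A reader might extend this to PFS, because the SAP censors patients who stop treatment for an adverse event. The documents do not support that step. The recurrence row governs everolimus, and Section 6 has anti-estrogen therapy continue after everolimus stops if the patient is deriving clinical benefit. Nothing here shows that the primary PFS analysis is at risk.

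**What to change.** Reconcile the Table 4 recurrence row with Table 4's first row and with Section 6.2.6. The clarification should state:

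- whether an interruption applies before the step-down and, if so, to what recovery level;
- which passage governs when more than one matches, including a late recurrence that resolves within 7 days;
- which recurrence the closing sentence on considering discontinuation refers to.

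The clinical choice is the sponsor's. The cost is one table row in a protocol clarification, with no added procedures or patients.
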